6.2.3 Premature Termination of the Study

Both the Investigator and the Sponsor reserve the right to terminate the study at any time. In this event, any necessary procedures will be arranged on an individual study basis after review and consultation by both parties. In terminating the study, the Sponsor and the Investigator will ensure that adequate consideration is given to the protection of the subjects'/patients' interests.

Regulatory authorities and IECs/IRBs should be informed in accordance with national regulations. Early termination of the study as a whole or by center may apply for the following reasons:

6.2.3.1 Early Termination of the Entire Clinical Study

At any time, the study as a whole will be terminated prematurely if new toxicological or pharmacological findings or safety reports invalidate the earlier positive benefit-risk-assessment.

6.2.3.2 Early Termination at an Individual Study Center

At any time, the study can be terminated at an individual center if:

- The center cannot comply with the requirements of the protocol.
- The center cannot comply with GCP standards.
- The required recruitment rate is not met.

Should the study be prematurely terminated, all study materials (completed and partially completed CRFs, IMPs, etc.) must be returned to the Sponsor.

7 ASSESSMENTS AND METHODS

7.1 Demographic and Baseline Information

The following information will be recorded during the Screening Visit (see Section 6.1.1):

7.1.1 Demographic and Baseline Characteristics

The demographic and baseline characteristics are age, ethnic origin, height, weight, CD4+ levels, and AB0 blood group (may also be derived from the patient's medical history). In addition, the Hemophilia Joint Health Score (HJHS) will be obtained (unless done within 3 months before the Screening Visit).

7.1.2 Medical History and Concomitant Medications

The medical history will be obtained by interviewing the patient's parents or guardians. Records of past diseases and treatments (e.g., hospital discharge letters) will be obtained for the study files, if available.

Concomitant medications will be also obtained by interview, and information about FVIII dosing in the previous 6 months will be collected.

The history or presence of FVIII inhibitor activity is an exclusion criterion (see Section 4.1.3).

7.2 Efficacy Assessments

This section summarizes the assessments to be performed for the calculation of the primary (see **Section 3.1.1**) and secondary endpoints (see **Section 3.1.2**) of this study.

7.2.1 Pharmacokinetic Evaluation

The following PK parameters for FVIII:C will be determined using a non-compartment model:

- AUC_{norm} and AUC
- In vivo half-life (T_{1/2})
- Maximum plasma concentration (C_{max})
- Time to reach maximum plasma concentration (T_{max})
- Mean residence time (MRT)
- Volume of distribution (Vd)
- Clearance (CL)
- Incremental in vivo recovery (IVR)

For details on the laboratory analyses, see Section 7.3.5.

7.2.2 IMP Administration Data

The following parameters will be documented:

- Dates and times of IMP injections
- Doses of IMP in IU and IMP batch numbers
- Purpose of IMP injection (PK, IVR, prophylaxis, treatment of BE, surgery)

7.2.3 Bleeding Episode (BE) Data

For any BE occurring during the study, the following data will be recorded:

- BE type (spontaneous, traumatic, postoperative, other)
- BE site
- BE severity (minor, moderate, major, life-threatening) (see **Table 1**)
- Date and time the BE first occurred or was first noticed
- Date and time the BE ended
- IMP administration data (see Section 7.2.2)
- Assessment of the efficacy of treatment at the end of the BE (see Section 7.2.4)

If the treatment of a BE in one bleeding site is interrupted for more than 48 hours, two separate BEs will have to be recorded; if, in addition to the original bleeding site, another bleeding site is affected, these events will be recorded as separate BEs at any time.

All of these parameters will be documented by the patient (together with the Investigator in case of on-site treatments) in the patient diary. Patients who experience a major or life-threatening BE should be treated at the study site, if possible.

Based on these data, the frequency of BEs and the ABR under prophylactic treatment will be calculated.

Table 1 Categorization for the Severity of Bleeding Episodes

Severity	Definition	Example	
Minor	Bleeding with few symptoms	Early onset muscle and joint bleeds with no visible symptoms, such as little or no change in the range of motion of affected joint (if joint bleeding event); mild restriction of mobility and activity, scrapes, superficial cuts, bruises, superficial mouth bleeds, and most nose bleeds	
Moderate	Bleeding that involves swelling or pain, including some decrease in range of motion of affected joint (if joint bleeding event) or moderate decrease in mobility and activity	Advanced soft tissue and muscle bleeds into the limbs, bleeding into the joint space, such as the elbow, knee, ankle, wrist, shoulder, hip, foot, or finger	
Major	Bleeding that causes significant pain, substantial decrease in range of motion of affected joint (if joint bleeding event), and incapacity	Complicated joint bleeds, bleeds of the pelvic muscles, eyes	
Life- threatening		Bleedings in the abdomen, digestive system or chest, central nervous system bleeds, bleedings in the area of the neck or throat or pharynx, or other major trauma	

7.2.4 Efficacy of the Treatment of Breakthrough BEs

At the end of a BE, treatment efficacy will be assessed by the patient (together with the Investigator in case of on-site treatment) using the predefined criteria detailed in **Table 2**.

Table 2 Efficacy Assessment of the Treatment of Breakthrough BEs

Excellent	Abrupt pain relief and/or unequivocal improvement in objective signs of bleeding within approximately 8 hours after a single injection		
Good	Definite pain relief and/or improvement in signs of bleeding within approximately 8–12 hours after an injection, requiring up to 2 injections for complete resolution		
Moderate	Probable or slight beneficial effect within approximately 12 hours after the first injection, requiring more than 2 injections for complete resolution		
None	No improvement within 12 hours, or worsening of symptoms, requiring more than 2 injections for complete resolution		

The **proportion of BEs successfully treated with IMP** will be evaluated for all BEs taken together and by BE severity. All efficacy ratings assessed as either 'excellent' or 'good' will be considered 'successfully treated.'

7.2.5 Surgical Prophylaxis Data

The following surgery-related parameters will be documented:

- Body weight within 12 hours before the start of surgery
- Safety laboratory tests (hematology, chemistry) within 12 hours before the start of surgery and 24 hours after the end of surgery (see **Section 7.3.5.2**)
- Vital signs within 12 hours before the start of surgery (before blood sampling)
- Type of surgery (planned or emergency)
- Location of surgery
- Severity of surgery (minor, major) (see definitions under (a) below)
- Expected duration of surgery
- Actual duration of surgery (start and end times, i.e., skin to skin)
- Details on IMP dose(s) given pre-, intra-, or postoperatively (see Section 7.2.2)
- Pre-, intra-, and postoperative FVIII plasma levels (see definitions under (b) below)
- Expected and actual blood loss (see item (d) below)
- Presence of wound hematomas and whether or not they require surgical evacuation
- Efficacy assessments at the end of surgery by surgeon (see Section 7.2.6.1)
- Efficacy assessment at the end of the postoperative period by hematologist (see Section 7.2.6.2)
- Overall efficacy assessment by the Investigator (see Section 7.2.6.3)
- Narrative describing the outcome and efficacy of the intervention
- Monitoring of AEs
- Details on concomitantly administered products, including any blood or blood product transfusions but excluding drugs given for routine anesthesia
- Inhibitor testing (see **Section 7.3.5.2**), with a plasma sample obtained within 3–8 weeks after the end of the surgery; this visit can coincide with another study visit with scheduled inhibitor testing.

(a) Severity of surgery

Surgeries are defined as **major** if any of the following criteria are met:

- General or spinal anesthesia required
- Opening into the great body cavities required
- Hemostatic therapy for at least 6 days required
- Orthopedic interventions involving joints (ankle, knee, hip, wrist, elbow, shoulder)
- 3rd molar extraction or extraction of \geq 3 teeth
- Surgeries/conditions in which the patient's life is at stake

The classification is made prospectively. All other surgeries are classified as **minor**.

(b) Definitions of periods and time points before, during, and after surgery

- **Preoperative** is defined as the time period of up to 3 hours before the start of surgery.
- The **end of surgery** is defined as the time immediately after the last surgical suture.
- Postoperative is the period from the end of surgery to the time the patient returns to his regular FVIII treatment regimen.
- The end of the postoperative period is the time the patient returns to his regular FVIII treatment regimen.

(c) FVIII plasma levels

FVIII plasma levels will be documented for the following time points:

- Immediately ($\leq 30 \text{ min}$) before and $30\pm15 \text{ min}$ after preoperative injection of IMP
- Immediately (≤ 30 min) before and 30 ± 15 min after each intraoperative bolus dose, if
- Immediately ($\leq 30 \text{ min}$) before and $30\pm15 \text{ min}$ after each postoperative dose, if any; in case of major surgery, the determination of FVIII plasma levels is mandatory for the first 3 postoperative doses

(d) Estimated and actual blood loss

Before surgery, the surgeon will provide written estimates of both the average and maximum volume (mL) of expected blood loss for the planned surgical procedure for a patient with normal hemostasis of the same sex, age, and stature as the patient enrolled in this study. After surgery, the surgeon will estimate the actual blood loss experienced by the patient.

7.2.6 Efficacy in Surgical Prophylaxis

Efficacy will be assessed at the end of surgery by the surgeon (see Section 7.2.6.1) and at end of the postoperative period by the hematologist (see Section 7.2.6.2). In both cases, predefined assessment criteria will be used.

In addition, there will be an overall assessment of efficacy (see Section 7.2.6.3).

7.2.6.1 At the End of Surgery (by Surgeon)

At the end of surgery, the hemostatic efficacy of Wilate will be assessed by the surgeon using the criteria listed in Table 3.

 Table 3
 Efficacy Assessment at the End of Surgery

Excellent	Intraoperative blood loss was lower than or equal to the average expected blood loss for the type of procedure performed in a patient with normal hemostasis and of the same sex, age, and stature.
Good	Intraoperative blood loss was higher than the average expected blood loss but lower or equal to the maximal expected blood loss for the type of procedure in a patient with normal hemostasis.
Moderate	Intraoperative blood loss was higher than the maximum expected blood loss for the type of procedure performed in a patient with normal hemostasis, but hemostasis was controlled.
None	Hemostasis was uncontrolled, necessitating a change in the clotting factor replacement regimen.

7.2.6.2 At the End of the Postoperative Period (by Hematologist)

At the end of the postoperative period, the hemostatic efficacy of *Wilate* will be assessed by the hematologist using the criteria listed in **Table 4**.

Table 4 Efficacy Assessment at the End of the Postoperative Period

Excellent	No postoperative bleeding or oozing that was not due to complications of surgery. All postoperative bleeding (due to complications of surgery) was controlled with Wilate as anticipated for the type of procedure.
Good	No postoperative bleeding or oozing that was not due to complications of surgery. Control of postoperative bleeding due to complications of surgery required increased dosing with Wilate or additional injections not originally anticipated for the type of procedure.
Moderate	Some postoperative bleeding and oozing that was not due to complications of surgery. Control of postoperative bleeding required increased dosing with Wilate or additional injections not originally anticipated for the type of procedure.
None	Extensive uncontrolled postoperative bleeding and oozing. Control of postoperative bleeding required use of an alternate FVIII concentrate.

7.2.6.3 Overall Efficacy Assessment at the End of the Postoperative Period (by Investigator)

Overall efficacy using the 'excellent,' 'good,' moderate,' and 'none' scale taking both the intraand postoperative assessments into account will be assessed by the Investigator.

Table 5 Algorithm for the Overall Efficacy Assessment for Surgical Prophylaxis

Intraoperative assessment	Postoperative assessment				
	Excellent	Good	Moderate	None	
Excellent	Excellent	Good	Good	Moderate	
Good	Good	Good	Moderate	Moderate	
Moderate	Good	Moderate	Moderate	None	
None	Moderate	Moderate	None	None	

7.3 Safety Assessments

7.3.1 Assessments for Safety Endpoints

Any of the following drug safety information shall be collected:

- Adverse events (AEs) and serious adverse events (SAEs) temporally associated with the administration of IMP (for definitions and reporting requirements, see Sections 7.3.2, 7.3.3, and 7.3.4)
- Drug overdose, interaction, medication error, and post-study SAEs (see Section 7.3.7)

7.3.2 Adverse Events (AEs)

7.3.2.1 Definitions

- Adverse event (AE): An AE is any untoward medical occurrence in a study subject/patient receiving an IMP and which does not necessarily have a causal relationship with this treatment. An AE can therefore be any unfavorable and unintended sign (including an abnormal laboratory finding), symptom, or disease temporally associated with the use of an IMP, whether or not related to the IMP.
- Treatment-emergent adverse event (TEAE): A TEAE is an AE that started or worsened after the start of IMP infusion.

- Adverse drug reaction (ADR): An ADR is any noxious and unintended response to an IMP related to any dose. The phrase 'response to an IMP' means that a causal relationship between the IMP and an AE carries at least a reasonable possibility, i.e., the relationship cannot be ruled out.
- Other significant AEs: Any marked laboratory abnormalities or any AEs that lead to an intervention, including withdrawal of drug treatment, dose reduction, or significant additional concomitant therapy.
- Withdrawal due to AE/ADR: AE/ADR leading to discontinuation of treatment with IMP. Any such events will be followed up by the Investigator until the event is resolved or until the medical condition of the subject/patient is stable. All follow-up information collected will be made available to the Sponsor.

7.3.2.2 Collection of AEs

The condition of the patient will be monitored throughout the study. At each visit, whether scheduled or unscheduled, AEs will be elicited using a standard nonleading question such as "How have you been since the last visit/during the previous study period?" In addition, the Investigator will check the patient diaries for any documented event.

Any AE or ADR which occurs during the study will be noted in detail on the appropriate pages of the CRF. If the patient reports several signs or symptoms representing a single syndrome or diagnosis, the diagnosis should be recorded in the CRF. The Investigator will grade the severity of all AEs or ADRs (mild, moderate, or severe), the seriousness (non-serious or serious), and the causality as defined in **Sections 7.3.2.3**, **7.3.3**, and **7.3.2.4**. The Sponsor is responsible for assessing the expectedness of each ADR (expected or unexpected) as defined in **Section 7.3.2.5**.

In the event of clinically significant abnormal laboratory findings, the tests will be confirmed and the patient followed up until the laboratory values have returned to normal and/or an adequate explanation for the abnormality has become available.

Diseases, signs and symptoms, and/or laboratory abnormalities already present before the first administration of IMP will not be considered AEs unless an exacerbation in intensity or frequency (worsening) occurs.

The Investigator will provide detailed information about any abnormalities and about the nature of and reasons for any action taken as well as any other observations or comments that may be useful for the interpretation and understanding of an AE or ADR.

7.3.2.3 Severity of AEs

The severity of AEs will be graded as follows:

- **Mild:** an AE, usually transient, which causes discomfort but does not interfere with the patient's routine activities
- **Moderate:** an AE which is sufficiently discomforting to interfere with the patient's routine activities
- **Severe:** an AE which is incapacitating and prevents the pursuit of the patient's routine activities

The grading of an AE is up to the medical judgment of the Investigator and will be decided on a case-by-case basis.

7.3.2.4 Causality of AEs

The relationship of AEs to the administered IMP will be assessed by the Investigator:

- **Probable:** reports including good reasons and sufficient documentation to assume a causal relationship, in the sense of plausible, conceivable, likely, but not necessarily highly probable. A reaction that follows a reasonable temporal sequence from administration of the IMP; or that follows a known or expected response pattern to the suspected medicine; or that is confirmed by stopping or reducing the dosage of the medicine and that could not reasonably be explained by known characteristics of the subject's/patient's clinical state.
- **Possible:** reports containing sufficient information to accept the possibility of a causal relationship, in the sense of not impossible and not unlikely, although the connection is uncertain or doubtful, for example because of missing data or insufficient evidence. A reaction that follows a reasonable temporal sequence from administration of the IMP; that follows a known or expected response pattern to the suspected medicine; but that could readily have been produced by a number of other factors.
- Unlikely: reports not following a reasonable temporal sequence from IMP administration. An event which may have been produced by the subject's/patient's clinical state or by environmental factors or other therapies administered.
- **Not related (unrelated):** events for which sufficient information exists to conclude that the etiology is unrelated to the IMP.
- **Unclassified:** reports which for one reason or another are not yet assessable, e.g., because of outstanding information (can only be a temporary assessment).

7.3.2.5 Classification of ADRs by Expectedness

ADRs will be classified by the Sponsor as either expected or unexpected:

- Expected: an ADR that is listed in the current edition of the Investigator's Brochure.
- **Unexpected:** an ADR that is not listed in the current edition of the Investigator's Brochure or that differs because of greater severity or greater specificity.

7.3.2.6 Outcome of AEs

The outcome of all reported AEs has to be documented as follows:

- 1. Recovered, resolved
- 2. Recovering, resolving
- 3. Not recovered, not resolved
- 4. Recovered, resolved with sequelae
- 5. Fatal
- 6. Unknown

NOTE: A patient's **death** per se is not an event, but an outcome. The event which resulted in the patient's death must be fully documented and reported, even in case the death occurs within 4 weeks after IMP treatment end and regardless of whether or not it is considered treatment-related.

7.3.2.7 Action(s) Taken

AEs requiring action or therapy must be treated with recognized standards of medical care to protect the health and wellbeing of the patient. Appropriate resuscitation equipment and medicines must be available to ensure the best possible treatment in an emergency situation.

The actions taken by the Investigator must be documented:

(a) General actions taken in the event of an AE

- None
- Medication (other than IMP) or other (e.g., physical) therapy started
- Test performed
- Other (to be specified)

(b) IMP-related actions taken in the event of an AE

- None
- Product withdrawn
- Dose reduced
- Dose increased

The Investigator will follow up on each AE until it has resolved or until the medical condition of the patient has stabilized. Any relevant follow-up information will be reported to the Sponsor.

7.3.3 Serious Adverse Events (SAEs)

A serious AE (SAE) is any untoward medical occurrence that at any dose:

- results in death,
- is life-threatening (see below),
- requires hospitalization or prolongation of existing hospitalization,
- results in persistent or significant disability/incapacity,
- is a congenital anomaly/birth defect,
- is another important medical event (see below).

NOTE: The term 'life-threatening' refers to an event in which the subject/patient was, in the view of the reporting Investigator, at immediate risk of death at the time of the event; it does not refer to an event which may hypothetically have caused death had it been more severe.

In deciding whether an AE/ADR is serious, medical judgment should be exercised. Thus, important AEs/ADRs that are not immediately life-threatening or do not result in death or hospitalization but may jeopardize the subject/patient or may require intervention to prevent one of the other outcomes listed in the definitions above should also be considered serious.

Examples of 'important medical events' are all suspected transmissions of an infectious agent, which therefore have to be reported as SAE. A suspected virus transmission means that virus antigen has been detected in the patient. A passive transmission of antibodies alone does not constitute a suspected virus transmission. Another such 'important medical event' that has to be reported as an SAE is the development of FVIII inhibitors.

7.3.4 AE and SAE Reporting Timelines

All **thromboembolic events**, whether or not they are suspected to be related to study treatment, are to be reported by telephone, fax, or email to the Clinical Trial Manager. They should be documented on AE page in eCRF.

After the Study Completion Visit, all thromboembolic events will continue to be monitored proactively by performing a Follow-up Contact 30 days after the completion visit (see **Section 6.1.7**). They should be documented on AE page in eCRF.

All **SAEs**, whether or not they are suspected to be related to study treatment, are to be reported immediately by telephone, fax, or email to the Clinical Trial Manager.

CLINICAL TRIAL MANAGER:

The contact details will also be communicated at the study initiation visit.

In addition, within 24 hours after recognition of an SAE, an Octapharma Serious Adverse Event Report must be completed and submitted to:

Waivers the from SAE Reporting Requirement

Waivers from the SAE reporting requirement include surgeries that are elective or were planned before study entry or prolongations of existing hospitalizations for economic or social, but not medical, reasons. Such surgeries or prolongations of hospitalizations should not be considered SAEs.

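### Protocol 7.3.4 takes elective surgery out of the SAEs with no exception for a condition that arose or worsened on Wilate, which, read literally, conflicts with 7.3.2 and 7.3.3

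*Protocol*

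**What the plan says.** The waiver is at the end of Protocol section 7.3.4 (AE and SAE Reporting Timelines): "Waivers from the SAE reporting requirement include surgeries that are elective or were planned before study entry". A second item in the same sentence waives "prolongations of existing hospitalizations for economic or social, but not medical, reasons". The section then states the effect: "Such surgeries or prolongations of hospitalizations should not be considered SAEs".

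The definitions are in the preceding sections:

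- 7.3.2.1: "An AE is any untoward medical occurrence in a study subject/patient receiving an IMP", and "A TEAE is an AE that started or worsened after the start of IMP infusion".
- 7.3.2.2: conditions already present before the first dose "will not be considered AEs unless an exacerbation in intensity or frequency (worsening) occurs".
- 7.3.3: an untoward occurrence is serious if, among other criteria, it "requires hospitalization or prolongation of existing hospitalization".

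Section 6.1.9 foresees that patients may have surgery during the study and may be admitted for it. Protocol 9.2.3 and SAP version 1.2 section 5.10.1 tabulate serious TEAEs and list SAEs. The SAP has no seriousness rule of its own, so it takes the classification as the sites record it.

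**The concern.** A waiver of this kind normally prevents an admission arranged for reasons unconnected with the study from being counted as harm. This one is wider. It does not ask when the need for surgery arose or whether the condition changed on treatment. An operation can be elective in timing and still be needed because of something that started or deteriorated on Wilate.

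In hemophilia this is a realistic case. Protocol 1.1 describes repeated joint bleeding with lasting sequelae, and 7.2.5 lists orthopedic interventions on joints among the major surgeries. If a child's joint deteriorates on prophylaxis and is then operated on electively, the definitions and the waiver point in opposite directions. Two sites could classify the same case differently, and both could cite the protocol. At stake are prompt sponsor review of the event and the serious-event count in a study of 10 children.

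**Working it through.** The plan gives no figure to reproduce. The check is a comparison of texts, followed by a small illustration.

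**1. Scope of the waiver.** The sentence has two limbs joined by *or*, each with its own verb: surgeries that *are* elective, or that *were* planned before entry. The time limit belongs grammatically to the second limb only. Elective surgery first decided on during treatment therefore falls under the first limb.

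**2. Effect of the waiver.** It is more than relief from expedited reporting. The sentence that follows says such surgeries are not to be considered SAEs, so a section on timelines also changes classification.

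**3. Limits on the waiver.** The prolongation item excludes medical reasons. The surgery item has no matching limit, and no other section of the protocol or SAP supplies one.

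**4. One case under each section.** Take a pre-existing joint problem that worsens after the first dose, with an elective operation decided on during the study that requires admission.

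| Section | Result |
|---|---|
| 7.3.2.2 (worsening of a pre-existing condition) | AE |
| 7.3.2.1 (worsened after the start of infusion) | TEAE |
| 7.3.3 (hospitalization criterion) | SAE; no exception for non-urgent admission |
| 7.3.4 (elective surgery) | Surgery not considered an SAE |

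Nothing in the documents says which of the last two rows prevails for the admission.

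**5. What is kept and what can be lost.**

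- Kept: the condition as an AE in the overall TEAE tables; the surgery data, AE monitoring and outcome narrative under 7.2.5; and the surgery tables and listings in SAP 5.9.
- At risk: the serious classification; the immediate notification and the 24-hour SAE report in 7.3.4; and entry in the serious-TEAE tables and SAE listings.
- Not a full replacement: the surgical efficacy ratings in 7.2.6 judge hemostasis during and after the operation, not why it was needed. Section 7.3.2.1 defines other significant AEs to include those leading to an intervention, but SAP 5.10.1 plans no table or listing for them.

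**6. Illustration of size.** Assume that exactly one patient has such an event and that there is no other serious TEAE. The exact 95% Clopper-Pearson limits are:

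- for x = 0: lower 0, upper 1 − 0.025^(1/n);
- for x = 1: lower 1 − 0.975^(1/n), upper the 0.975 quantile of Beta(2, n − 1).

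| n | Waiver applied literally | Classified under 7.3.3 |
|---|---|---|
| 10 (planned enrollment) | 0/10 = 0% (0 to 30.8%) | 1/10 = 10% (0.3 to 44.5%) |
| 8 (evaluable target) | 0/8 = 0% (0 to 36.9%) | 1/8 = 12.5% (0.3 to 52.7%) |

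The intervals are added here for scale. The plan specifies Clopper-Pearson intervals for inhibitor findings and parvovirus B19 seroconversion, not for AE incidence.

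**The case against.** The strongest reply is that the waiver names the surgery, not the condition behind it. An operation is not itself an untoward occurrence. The protocol separates events from their consequences elsewhere: death is treated as an outcome (7.3.2.6) and therapy as an action taken (7.3.2.7). On this reading the deteriorated joint remains an AE, the investigator still grades its seriousness, and 7.3.4 removes nothing. Section 7.3.3 also asks for medical judgment, lists significant disability as a separate criterion, and treats as serious an AE that may need intervention to prevent a serious outcome. Inhibitors and suspected virus transmission must be reported as SAEs, and thromboembolic events have their own reporting rule.

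Much of this stands. A careful investigator can reach the right classification, which is why the point is limited to the literal wording. But the protocol nowhere states the safer reading. The link between the condition and the hospitalization criterion is the admission for surgery, which is the item that 7.3.4 sets aside. The other criteria catch some cases, not all.

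A reader might infer several stronger things that the documents do not support:

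- **That every non-emergency operation is waived.** *Elective* is not defined. The planned/emergency split is a data field in 7.2.5 that is never tied to the waiver.
- **That such events disappear from the safety data, or that failed prophylaxis is hidden.** The events remain TEAEs. Bleeding under prophylaxis is measured by TABR and SABR, with each bleeding episode recorded under 7.2.3, although surgery periods and the bleeds within them are excluded from those rates.
- **That surgical complications are waived.** Only the surgeries themselves are named, and prolongation of a stay for medical reasons is expressly left outside the waiver.

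**Conclusion.** The conflict is real, but it is one of wording. Followed literally, 7.3.4 can take the serious flag off an admission that 7.3.3 would call serious, when the operation is elective and the condition is new or has worsened since the first dose. No other text resolves it.

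Its size cannot be derived from the documents. Section 6.1.9 says only that surgery may occur, and no number of such operations is given. If none occurs, no table changes and only the contradiction remains. If one patient is affected and the waiver is read literally, the serious-TEAE incidence among 10 patients is 10 percentage points lower than under 7.3.3, and the prompt reports are not triggered.

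The conclusion rests on protocol version 02, marked for Ukraine only. The cover of SAP 1.2 also lists a version 03 dated 2018-07-06, which was not available, so nothing is said here about its wording. The point merits correction because a stated rule, not merely a missing detail, produces the conflict and the correction is cheap.

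**What to change.** Amend the waiver paragraph in 7.3.4 as follows:

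1. Leave the waiver for prolongations for economic or social reasons as it is.
2. Limit the surgery waiver to elective or pre-planned surgery for a condition that was present before the first dose of IMP and has not worsened since. This still exempts an operation scheduled during the study for an unchanged pre-existing condition, which 7.3.2.2 does not treat as an AE.
3. Add that a new or worsened condition leading to surgery is still assessed for seriousness under 7.3.3, using that section's existing hospitalization criterion. The criterion should stay at *requires*; changing it to *involves* would widen the SAE definition.

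The cost is one short protocol amendment and possibly a few extra SAE forms. No visit, sample, procedure or planned analysis changes.
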